5. STATISTICAL METHODS

Descriptive statistical methods will be used to summarize the data from this study, with confidence intervals calculated for the primary and secondary efficacy endpoints. The term “descriptive statistics” refers to number of subjects (n), mean, median, standard deviation (SD), minimum, and maximum for continuous data and frequencies and percentages for categorical data. The term “treatment group” refers to randomized treatment assignment: Test and Reference. All data collected during the study will be included in data listings. The data will be sorted first by subject

number, and then by date within each subject number. Unless specified otherwise, all statistical testing will be two-sided and will be performed using a significance (alpha) level of 0.05.

All statistical analyses will be conducted with the SAS[®] System, version 9.4 or higher within a validated statistical computing environment.

5.1. Subject Disposition, Demographic and Baseline Characteristics

Subject disposition, including the number of subjects who completed the study, discontinued from the study, reasons for early discontinuation, and the number of days on study will also be provided and presented for all subjects randomized. Subject disposition will be summarized by treatment group. Additionally, study therapy compliance will be summarized by treatment group.

Demographic data and baseline characteristics including age, ethnicity, race, gender, and severity of itching and burning sensations will be summarized using appropriate descriptive statistics by treatment group for the mITT and PP populations. Descriptive statistics will be generated for continuous variables (e.g. age). The number and percentage of subjects in each class of categorical demographic and Baseline variables (e.g. gender, ethnicity, race, and severity of itching and burning sensation) will be tabulated by treatment group and population (mITT and PP) for Baseline (Visit 2 or Visit 1 if applicable). Individual subject demographic and Baseline characteristics data will be listed. No inferential testing will be performed.

5.2. Efficacy Analyses

5.2.1. Primary Efficacy Endpoint

The primary endpoint will be the proportion of patients that are identified as cured at the end of the treatment period on Study Day 28 (Visit 5). Cure is defined as the absence of new lesions and the healing of all old lesions. Residual, dry, non-inflammatory papules are not counted as active. Descriptive statistics (number of subjects, number of subjects cured, and proportion of cured) for the primary efficacy variable will be tabulated by treatment group and population (mITT and PP). The results for the PP population will be considered definitive with those in the mITT population as supportive.

5.2.3. Secondary Efficacy Endpoints

The secondary endpoint will be the proportion of patients that are identified as cured at the end of the treatment period on Study Day 14 (Visit 4). Descriptive statistics (number of subjects, number of subjects cured, and proportion of cured) for the secondary efficacy variable will be tabulated by treatment group and population (mITT and PP). The results for the PP population will be considered definitive with those in the mITT population as supportive.

5.2.4. Secondary Efficacy Analyses

As a secondary endpoint evaluation, patients' clinical progress at Visit 4 (Day 14) will be assessed and proportion of cured patients in treatment arms will be compared using the procedure described

in the analysis of the primary efficacy endpoint.

5.3. Tolerability Assessment

Subjects' self-assessment of itching and stinging/ burning sensations during screening and treatment periods (Visits 2 through 5) will be used to assess tolerability to the study treatments. Itching is defined as intense, distracting irritation or tickling sensation in the last 24 hours and is evaluated on a scale from 0 (No Itching) to 4 (Unbearable, Intense Itch). Stinging/ burning is defined as sensation of the skin is painfully hot or noticeable tingling sensation in the last 24 hours and is evaluated on a scale from 0 (Absent) to 3 (Marked, Intense).

Descriptive statistics using categorical methods will be used to compare tolerability measures between the test and reference treatment groups and various study days (e.g. Baseline (Visit 2), Visit 3, Visit 4, and Visit 5). Tolerability analyses will be presented for mITT and PP populations.

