### 8.1 Subject Population/Data Sets to Be Evaluated

The subject populations are defined as follows:

1. **Safety Population:** The safety population is any randomized individual who (a) was enrolled into the study, and (b) received at least one dose of study treatment.
2. **Modified Intent-to-Treat (mITT) Population:** A modified intent-to-treat subject is any randomized individual who (a) met inclusion/exclusion criteria, (b) was enrolled into the study, (c) received at least one dose of the assigned study treatment, and (c) had at least one post-baseline visit.
3. **Per Protocol (PP) Population:** A per-protocol subject is any randomized individual who (a) met inclusion/exclusion criteria, (b) was enrolled into the study, (c) received the assigned study treatment, (d) had not taken any concomitant medications prohibited by the protocol or experienced any major deviations that interfered with or may have interfered with the therapeutic administration of the treatment or the precise evaluation of treatment efficacy, and (e) completed the primary endpoint evaluation within the designated visit window ( $\pm 4$  days).

Subjects whose condition worsens and require alternate or supplemental therapy for the treatment of scabies during the study will be discontinued, included in both the mITT and PP population analyses as treatment failures. Subjects who discontinue early for reasons other than treatment failure will be excluded from the PP population, but included in the mITT population, using Last Observation Carried Forward (LOCF).

Efficacy analyses will be performed using the per-protocol population as definitive and the mITT population as supportive. Safety analyses will be performed using the Safety population.

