### **8.3.4 Assessment of Tolerability**

Descriptive statistics using categorical methods will be used to compare tolerability measures (scores of Stinging/Burning and Itching sensations collected during Patient Self-Assessments) between the test and reference treatment groups.

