2. OBJECTIVES

The primary objective of this study is:

- To demonstrate bioequivalence between Permethrin Cream, 5% (Mayne Pharma, Inc.) and Elimite™ in patients with active scabies.

The secondary objective of this study is:

- To demonstrate comparative safety of Permethrin Cream, 5% (Mayne Pharma, Inc.) vs Elimite™ and tolerability of 5% Permethrin cream.

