4. ANALYSIS POPULATIONS

The populations defined for analysis will include the modified intent-to-treat (mITT), per-protocol (PP), and the safety population.

Safety population: The safety population is any randomized individual who: (a) was enrolled into the study, and (b) received at least one application of study treatment. Subjects will be analyzed according to the treatment received. This population will be used for safety assessment.

Modified Intent-to-Treat (mITT): A modified intent-to-treat subject is any randomized individual who: (a) was enrolled into the study, (b) met inclusion/exclusion criteria, (c) received at least one application of study treatment, and (d) had at least one post-baseline visit. Subjects will be analyzed according to the randomized treatment. This population will be used for secondary and primary efficacy analysis as supportive analysis.

Per Protocol (PP): A per-protocol subject is any randomized individual who: (a) enrolled into the study and met inclusion/exclusion criteria, (b) received the assigned study treatment, (c) had not taken any concomitant medications prohibited by the protocol or experienced any major deviations that interfered with or may have interfered with the therapeutic administration of the treatment or the precise evaluation of treatment efficacy, and (d) completed the primary endpoint evaluation within the designated visit window (± 4 days).

Subjects whose condition worsens and require alternate or supplemental therapy for the treatment of scabies during the study will be discontinued, included in both the mITT and PP population analyses as treatment failures. Subjects who discontinue early for reasons other than treatment failure will be excluded from the PP population, but included in the mITT population, using Last Observation Carried Forward (LOCF).

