8. TABLES, LISTINGS AND FIGURES

Tables

1. Summary of Subject Enrollment and Disposition.
2. Summary of Subject Demographics at Screening (mITT population).
3. Summary of Subject Demographics at Screening (PP Population).
4. Summary of Medical History/Other Concomitant Illness at Screening.
5. Summary of Physical Exam Abnormalities.
6. The proportion of patients that are identified as cured on Study Day 28 (Visit 5) (mITT population).
7. The proportion of patients that are identified as cured on Study Day 28 (Visit 5) visit (PP population).
8. Summary of Visual examination at each visit (mITT population).
9. Summary of Visual examination at each visit (PP Population).
10. The proportion of patients that are identified as cured on Study Day 14 (mITT population).
11. The proportion of patients that are identified as cured on Study Day 14 (PP population).
12. Summary of self-assessment of itching and stinging/ burning sensations at each visit (mITT population).
13. Summary of self-assessment of itching and stinging/ burning sensations at each visit (PP population).
14. Summary of change of self-assessment of itching and stinging/ burning sensations from baseline at each visit (mITT population).
15. Summary of change of self-assessment of itching and stinging/ burning sensations from baseline at each visit (PP population).
16. Adverse Events by System Organ Class and Preferred Term.
17. Adverse Events with incidence >5 % by System Organ Class and Preferred Term.
18. Treatment Emergent Adverse Events by System Organ Class and Preferred Term.
19. Treatment Emergent Adverse Events by maximum Severity.
20. Summary of Treatment Emergent Adverse Events possible or probably related to the study drug.
21. Summary of Serious Adverse Events by System Organ Class and Preferred Term.
22. Summary of Concomitant Medications.

Data Listings

1. Listing of Analysis Population and Study Completion.
2. Listing of Subjects Who Discontinued.
3. Listing of Patients Excluded from Per Protocol Efficacy Analysis.
4. Listing of Protocol Deviation.
5. Listing of Subject Demographics.
6. Listing of Drug Accountability.
7. Listing of Visual Examination.
8. Listing of Subject Diary data.
9. Listing of Patient Self-assessment.
10. Listing of Adverse Events.
11. Listing of Treatment Emergent Adverse Events.
12. Listing of Non-Treatment Emergent Adverse Events.
13. Listing of Adverse drug reaction.

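### Tolerability is presented only in mITT and PP; an as-treated Safety-population version would be a near-free improvement

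*SAP*

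**What the plan says.** Tolerability is part of the single secondary objective, which SAP 2 gives as "To demonstrate comparative safety of Permethrin Cream, 5% (Mayne Pharma, Inc.) vs Elimite™ and tolerability of 5% Permethrin cream".

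SAP 5.3 fixes the analysis sets: "Tolerability analyses will be presented for mITT and PP populations". The list in SAP 8 matches. Tables 12 and 13 summarise the scores by visit, and Tables 14 and 15 summarise change from baseline. Figures 3 to 6 plot the scores. Each output exists in an mITT and a PP version; Table 13, for example, is "Summary of self-assessment of itching and stinging/ burning sensations at each visit (PP population". No tolerability table or figure uses the Safety population.

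Protocol 8.3.4 gives the method ("Descriptive statistics using categorical methods will be used to compare tolerability measures") but no population. Protocol 8.1 says "Safety analyses will be performed using the Safety population".

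SAP 4 defines the sets:

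- **Safety:** randomised, enrolled, at least one application. "Subjects will be analyzed according to the treatment received. This population will be used for safety assessment".
- **mITT:** also requires that eligibility criteria were met and that there was a post-baseline visit. "Subjects will be analyzed according to the randomized treatment".
- **PP:** requires, among other things, receipt of the assigned treatment, no prohibited medication and no major deviation. "Subjects who discontinue early for reasons other than treatment failure will be excluded from the PP population"; the same sentence goes on to keep them in mITT.

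Protocol 6.2.3 says the self-assessment scores are not recorded as adverse events. SAP 5.4 limits the safety endpoints to adverse events and vital signs.

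**The concern.** A tolerability summary should include everyone who used the product, under the product they used. PP membership depends on what happens after application, and some of that may follow from irritation or itch: leaving the study, taking an antipruritic too close to a visit, or washing the cream off early. A PP table therefore tends to lose the subjects with the worst scores. If one product irritates more than the other, it also tends to narrow the difference between arms.

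Because the scores are kept out of adverse event records, the as-treated adverse event tables do not carry them. The mITT and PP outputs are the only planned comparison of these data between arms. The Safety set, which avoids the selection, is already defined but is not used here.

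**Working it through.** **1. The plan's own figures.** Both sample sizes reproduce. Exact enumeration with the continuity-corrected 90% interval of Protocol 8.3.2 gives power 0.817 at 56 per group (88% vs 88%) and 0.952 at 91 per group (86% vs 88%). Enrolment with 20% not qualifying for PP (Protocol 8.2):

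- 56 / 0.80 = 70 per group, 140 in total; planned PP loss 140 − 112 = 28 (20%).
- 91 / 0.80 = 113.75, rounded up to 114 per group, 228 in total; planned PP loss 228 − 182 = 46 (20.2%).

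These losses cover ineligibility, prohibited medication, major deviations, missed windows and every early exit. They do not estimate exits for local reactions, for which the documents give no figure.

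**2. Who is in each set.** Applying SAP 4 to treated subjects:

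| Treated subject | Safety | mITT (SAP) | PP |
|---|---|---|---|
| Leaves early for a local reaction; eligible; has a post-baseline visit | in | in | out |
| Found not to meet an eligibility criterion | in | out | out |
| Given the wrong product | in, under product received | in, under randomised arm | out |
| No post-baseline visit | in | out | out |

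The last row matters little, since such a subject has no post-baseline score. In the third row, the protocol's mITT definition (8.1) requires the assigned treatment and would exclude the subject; the SAP omits that word.

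**3. Which ineligible subjects matter.** Protocol 4.2.2, exclusion 8, covers sensitivity to permethrin or the cream's components. A treated subject later found to meet it is highly relevant to tolerability, yet leaves mITT. Exclusion 3 includes topical antipruritics and oral antihistamines within 24 hours of any study visit. Read literally, use near a later visit is also an eligibility failure. Such cases are foreseeable: Protocol 5.8.1 lets antipruritics be prescribed subject to those windows, 5.11 allows approved continuation after a prohibited medication, and 10.3.2 allows eligibility deviations with written approval. No number is given.

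**4. Routes out of PP that irritation or itch could cause.** These are discontinuation for an adverse event (Protocol 4.3), an antipruritic or antihistamine within 24 hours of a visit (5.11), and washing the cream off within 8 hours (5.9), if that is judged a major deviation.

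**5. Illustration of the PP effect.** Assume that 7 of 70 subjects in an arm have marked stinging (10%), that k of those 7 leave PP, and that nobody else does. The PP rate is (7 − k) / (70 − k):

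- k = 1: 6/69 = 8.7%
- k = 3: 4/67 = 6.0%
- k = 5: 2/65 = 3.1%
- k = 7: 0/63 = 0%

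If all 70 are eligible and have a post-baseline visit, the mITT and Safety rates both stay at 10%. The 7 of 70 is assumed, not taken from the documents.

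**The case against.** The strongest reply is that the mITT tables already do most of the work. Early leavers stay in mITT, and Protocol 6.3.5 gives them a self-assessment at the early termination visit. A reader can set Table 12 beside Table 13 and see any selection. This stands: a reader might infer that these subjects vanish from all tolerability output, and they do not.

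Nor is there a conflict with the protocol. Both documents list tolerability apart from safety (Protocol 2.3 and 2.4, 8.3.4 and 8.3.5; SAP 5.3 and 5.4). The statement in Protocol 8.1 about safety analyses therefore need not cover it, and the SAP fills a gap. This also stands.

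A reader might further infer that nothing is analysed as treated. That is too broad. Adverse events and vital signs use the as-treated Safety set, and in PP the assigned and received products coincide by definition. The accurate statement is that no tolerability table or figure places a mis-dispensed subject under the product received.

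Local reactions are not invisible either. The diary asks about them, subjects are queried about adverse events, and events leading to discontinuation are summarised (SAP 5.4.1). The scores themselves are in Listing 9, and SAP 7 prepares listings for all subjects.

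Finally, itching is also a symptom of scabies and may persist after successful treatment (Protocol 1.1 and 5.8.1), so showing it in the efficacy sets is defensible. That is a reason to keep those versions, but not a reason to leave out the Safety set.

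**Conclusion.** The point holds as a minor one. Tolerability belongs to the secondary objective, yet its tables and figures use only mITT and PP. PP selects on a consequence of poor tolerability. mITT largely repairs that, but loses treated subjects who failed eligibility and, under the SAP wording, groups a mis-dispensed subject by randomised arm.

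The expected difference between Safety and mITT tables is small and cannot be quantified from the documents. It depends on how many treated subjects are ineligible or mis-dispensed, and on how literally exclusion 3 is applied to later visits. It would be wrong to take 28 of 140 or 46 of 228 as the size of the problem: they are all-cause planning allowances, and they concern PP only. The analyses are descriptive, so no test, sample size or bioequivalence conclusion is affected.

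**What to change.** In SAP 5.3, name the Safety population, grouped by treatment received, as the main set for tolerability. In SAP 8, produce Tables 12 and 14 and Figures 3 and 5 in that set. Keep the mITT and PP versions (including Tables 13 and 15 and Figures 4 and 6) only as supplementary, and label them so. While editing, settle whether mITT requires receipt of the assigned treatment, since Protocol 8.1 and SAP 4 differ on that word.

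The cost is a few extra or re-populated descriptive outputs. No new data are needed, and the sample size and primary analysis do not change.

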5.4. Safety Assessment

Safety analyses will be presented for the Safety Population, defined as all subjects who receive at least one dose of study medication. Adverse events and vital signs measurements will be used as safety endpoints and summarized by treatment group. The previous and concomitant medications will also be summarized.

5.4.1. Adverse Events

Analysis of adverse events as safety variables will be based on all adverse event (AE) capture measuring severity and frequency utilizing MedDRA terminology for consistency. AEs will be mapped to a MedDRA-preferred term and system organ classification. If a subject experiences multiple events that map to a single preferred term, the greatest severity and strongest Investigator assessment of relation to study drug will be assigned to the preferred term for the appropriate summaries. Should an event have a missing severity or relationship, it will be classified as having the highest severity and/or strongest relationship to study drug.

Summaries of treatment-emergent AEs will include any AEs reported beginning with the first dose of study drug on Day 1. The occurrence of treatment-emergent adverse events will be summarized by treatment group using preferred terms, system organ classifications, and severity. Separate summaries of treatment-emergent serious adverse events (SAEs), treatment-emergent adverse events related to study drug, and events leading to the discontinuation of study drug will be generated.

All AEs will be listed for individual subjects showing both verbatim and preferred terms.

5.4.2. Vital Signs

Vital signs will be collected at the Screening visit; on the Baseline, and at visit 5 (or upon subject discontinuation). Vital signs will include body temperature (oral), heart rate and blood pressure (systolic and diastolic). Any abnormal characteristics will be evaluated by the Investigator based on their clinical significance. Abnormal vital signs will be considered AEs if they require therapeutic medical intervention, and/or if the Investigator considers them to be AEs due to the clinical judgement.

5.4.3. Previous and Concomitant Medications

Concurrent medications and any medications taken in the 30 days prior to the start of the study will be recorded as prior/concomitant medications (using their generic and brand name, if known) with the corresponding indication. Concomitant medications will be coded using the WHO dictionary. These data will be summarized by treatment group. Previous and concomitant medications will be presented in a data listing.

6. CHANGES IN THE PLANNED ANALYSES

No deviations in the conduct of the study or the planned analysis are anticipated. Should any deviations from the analyses specified in the authorized statistical analysis plan arise, such deviations will be documented in the final clinical study report.

7. PROGRAMMING CONVENTIONS

Statistical programs will be developed using SAS® version 9.4 or higher. Programs will be documented, produced, and validated. Additionally, the following conventions should be incorporated:

- Page orientation, margins, and fonts: Summary tables, listings, and figures will appear in landscape orientation. There should be a minimum of a 1.25” boundary on the upper (bound) edge, and a minimum of a 1.0” boundary on the remaining three edges. Output should be printed in Courier New with a point size of at least 8. Titles may be printed using a larger font (e.g., Arial point size 10).
- Identification of analysis population: Every summary table and figure should clearly specify the analysis population being summarized. Listings will be prepared for all subjects.
- Group headers: In the summary tables, the group headers will identify the treatment group and the within-group sample size for the indicated analysis population. Of note, the header’s sample size does not necessarily equal the number of subjects summarized within any given summary module; some subjects in the analysis population may have missing values and, thus, may not be summarized.

-
- Suppression of percentages corresponding to null categories: When count data are presented as category frequencies and corresponding percentages, the percent should be suppressed when the count is zero in order to draw attention to the non-zero counts.
 - Presentation of sample sizes: Summary modules should indicate, in one way or another, the number of subjects contributing to the summary statistics presented in any given summary module. As mentioned above, this may be less than the number of subjects in the analysis population.
 - ◆ In the quantitative modules describing continuous variables (and thus presenting sample size, means, and standard deviations), the sample size should be the number of non-missing observations.
 - ◆ For categorical variables that are presented in frequency tables, the module should present the total count in addition to the count in each category. Percentages should be calculated using this total as the denominator, and the percentage corresponding to the sum itself (that is, 100%) should be presented to indicate clearly to a reviewer the method of calculation. Missing data will not contribute to the calculation of percentages.
 - Sorting: Listings will be sorted by treatment group, subject identification number and date, if applicable. If a listing is sorted in a different manner, a footnote will indicate as such.
 - General formatting rules: Rounding for all variables will occur only as the last step, immediately prior to presentation in listings, tables, and figures. No intermediate rounding will be performed on derived variables. The standard rounding practice of rounding numbers ending in 0-4 down and numbers ending in 5-9 up will be employed.
 - The presentation of numerical values will adhere to the following guidelines:
 - ◆ Raw measurements will be reported to the number of significant digits as captured electronically on the eCRFs.
 - ◆ Standard deviations will be reported to one decimal place beyond the number of decimal places the original parameter is presented.
 - ◆ Means will be reported to the same number of significant digits as the parameter, unless the parameter is an integer, then 1 decimal place will be reported.
 - ◆ Calculated percentages will be reported with no decimals.
 - Dates will be formatted as DDMMMYYYY. Partial dates will be presented on data listings as recorded on CRFs.
 - Time will be presented according to the 24-hour clock (HHMM).

